10.1.3 Reporting Adverse Events

The patient will be given instructions to record AEs on their eDiary and will be asked about AEs at the clinic visit on Day 12 and on the telephone visit at Day 28. In addition, the investigator should review AEs reported in the eDiary employed in the study.

When recording an AE, the investigator should use the overall diagnosis or syndrome using standard medical terminology, rather than recording individual symptoms or signs. The eCRF and source

documents should be consistent. Any discrepancies between the patient's own words on his/her own records (e.g., eDiary entry) and the corresponding medical terminology should be clarified in the source documentation.

Details for completion of the Adverse Event CRF (including judgment of relationship to investigational device or study procedure) are described in the eCRF Completion Guidelines.

10.1.3.1 Data Safety Monitoring Board (DSMB)

An independent DSMB of external advisors will meet prior to the start of the study, and periodically during enrollment and follow-up and at trial end to review safety data. The Board will be blinded to patients' actual randomized group assignments but may request at any time that the blind be broken by the data center, if concerns arise from the blinded data. Ad hoc meetings will be convened if SAEs occur that are considered at least possibly related to the investigational product.

The subject will be given the opportunity to report AEs spontaneously. A general, nonleading, prompt will also be given at each study visit and during each study phone call to solicit AEs.

When recording an AE, the investigator should use the overall diagnosis or syndrome, using standard medical terminology, whenever possible, rather than recording individual symptoms or signs. The eCRF and source documents should be consistent. Any discrepancies between the subject's own words on his/her own records (e.g., diary card) and the corresponding medical terminology should be clarified in the source documentation.

Details for completion of the Adverse Event eCRF (including the judgment of relationship to investigational product or study procedure) are described in the eCRF Completion Guidelines (CCGs).

10.1.3.2 Adverse Event and Serious Adverse Event Reporting Procedures

- Safety Contact Information:

Drug Safety Navigator (DSN)

Email: [contact]

- AE Reporting:

AEs occurring (initial occurrence or a worsening of a pre-existing condition) after the subject signs the informed consent form and up to the final follow-up visit at Day 28 will be reported and included in the study database.

AEs will be reported on the AE CRF Form, and any related questions should be directed to DSN.

- SAE Reporting:

Any SAE experienced from the time the subject signs the informed consent up to the final follow-up visit at Day 28 will be reported to DSN as described below. Additionally, SAEs that occur after completion of the Follow-up period will also be reported to DSN if the Investigator considers the SAE related to study drug.

SAEs must be reported to DSN within 24 hours of the Investigator's (site's) awareness or notification of the event. To report the SAE, the site must complete the SAE Form for the study. This form is not part of the eCRF and will be provided separately to the Investigator by DSN. Initial and follow-up

SAE reports will be sent to DSN via email to [contact], and to the sponsor's Chief Medical Officer and to the Medical Monitor.

The SAE reporting should not be delayed, and the sites may call and provide the available SAE information within 24 hours of Investigator's awareness. A written SAE Form should be sent via email to [contact], as soon as possible.

The Investigators should make every effort to provide complete information on the SAE Form. At the minimum, the initial SAE report must contain the subject's identifiers, event term as known, SAE criterion and the Investigator's causality assessment. Additional information (or updates to the previously reported information) may be provided, as it becomes available through a follow-up SAE report.

The Investigator must continue to follow the subject until the SAE resolves, the condition becomes chronic in nature, stabilizes (in the case of persistent impairment), or the subject dies. Within 24 hours of receipt of follow-up information, the Investigator must complete the SAE Form and submit any supporting documentation, as necessary (e.g., laboratory test reports, subject discharge summary, or autopsy reports) to DSN via email to [contact].

The Investigator is also required to submit SAE reports to the IRB in accordance with applicable requirements.

10.2 Pregnancy and Birth Control

All females should use an acceptable method of birth control (to be recorded on a source document and eCRF). Since a fetus would have an unknown G6PD status, TQ should not be used in pregnant women or in lactating mothers with infants of deficient or unknown G6PD status. If a patient becomes pregnant during the study or within 56 days of discontinuing study medication, the Investigator should report the pregnancy to Medical Monitor within 24 hours of being notified. CRO personnel will then forward the Exposure In Utero form to the Investigator for completion.

The patient should be followed by the Investigator until completion of the pregnancy. If the pregnancy ends for any reason before the anticipated date, the Investigator should notify the Medical Monitor. At the completion of the pregnancy, the Investigator will document the outcome of the pregnancy. If the outcome of the pregnancy meets the criteria for immediate classification as an SAE (i.e., spontaneous abortion, stillbirth, neonatal death, or congenital anomaly), the Investigator should follow the procedures for reporting an SAE.

10.3 Overdose of Investigational Medicinal Product

Excessive dosing (beyond that prescribed in the protocol and including overdose) should be recorded in the CRF. Any SAE or nonserious AE associated with excessive dosing must be followed as any other SAE or nonserious AE. These events are only considered AEs or SAEs if there are associated clinical signs and symptoms or if the act of taking the excess medicine itself is an AE or SAE (e.g., suicide attempt).

There is no experience of acute overdose with TQ, and management should be as clinically indicated. Hemolytic anemia and methemoglobinemia have been observed in clinical studies and are likely to be encountered in overdose.

10.4 Safety Signal Detection

Selected data from this study will be reviewed periodically to detect as early as possible any safety concern(s) related to TQ so that investigators, patients, regulatory authorities, and IRBs/IECs will be informed appropriately and as early as possible.

The Medical Monitor or medically qualified designee/equivalent will conduct an ongoing review of SAEs and perform ongoing SAE reconciliations in collaboration with the safety group representative.

TQ should be discontinued immediately, if signs of hemolysis (anemia, dark colored urine) or methemoglobinemia (cyanosis) develop during administration. Due to the risk of hemolytic anemia in patients with G6PD deficiency, G6PD testing must be performed before administering TQ. Due to the limitations of G6PD tests, physicians need to be aware of residual risk of hemolysis, and adequate medical support and follow-up to manage hemolytic risk should be available. In clinical studies, declines in hemoglobin levels were reported in some G6PD-normal patients. Monitor patients for clinical signs or symptoms of hemolysis.

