On Day 1, eligible patients will either return to the clinic or may have a telemedicine visit. Continued eligibility will be reviewed, and if still eligible, patients will be randomized and will receive and self-administer 200 mg TQ or matching placebo on Days 1, 2, 3, and 10 (each administration of drug will be within \pm 1 day with the exception of the first dose). If the Day 1 visit is a telemedicine visit, the randomized blinded study drug will be couriered to the patient. Patients will be provided an oral thermometer to check and record their daily temperature and a home pulse oximeter to record their daily oxygen saturation. Patients will also be provided with an electronic study diary (eDiary) (loaded onto a device of their choosing) and be required to complete the eDiary entries from Day 1 through Day 12 [\pm 1 day]. Patients will record respiration rate, temperature, COVID-19 clinical signs including presence and severity of cough, respiration rate and shortness of breath, AEs, and concomitant medications in the electronic diary daily. They will also record study drug administrations in the diary to monitor compliance. Daily diary data will be automatically uploaded to the electronic data management system and will be reviewed daily by clinical staff.

Patients will be contacted by telephone or videoconferencing by designated study personnel on a daily basis to review AEs for severity by asking an open ended question, check for use of concomitant medications, and if there are new or worsening signs and symptoms of COVID-19 disease from Day 1 through Day 11 [\pm 1 day]. Telemedicine interviews will follow a script and information will be recorded in source documents. If a suspected SAE or worsening of signs and symptoms of COVID-19 are reported, a study physician will be contacted to determine if the patient needs additional support (clinic visit, medication, or emergency room visit). If the patient cannot be reached an individual from their emergency contact list will be contacted to determine if the patient has been hospitalized. Patients will return to clinic on Day 12 [\pm 1 day] for the assessments listed in [Table 1](#). From Day 13 [\pm 1 day] through Day 28 [\pm 1 day], patients will be instructed to complete the eDiary and will have a final telemedicine call on Day 28 [\pm 1 day].

The schedule of study procedures is illustrated in [Table 1](#).

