6.2 Schedule of Study Assessments

Table 1 Schedule of Procedures

Procedure	Screening Day -4 to -1	Day 1	Day 1	Days 2 and 3 ± 1 day	Days 4 to 9	Day 10 ± 1 day	Day 11	Day 12 ± 1 day	Day 28 ± 1 day
Clinic Visit #	1	If in clinic	If at home					2 or 3	
Informed consent	X								
Eligibility criteria	X	X	X						
Pregnancy testing ¹	X							X	
Demography	X								
Medical history	X	updated	updated						
G6PD test	X								
Physical exam	X							X	
Vital signs ²	X							X	
Clinical symptoms of COVID-19 ³									
Temperature ⁴	X	X	Self-measured by patient daily and recorded in eDiary					X	
Respiration rate ⁵	X	X	Self-measured by patient daily and recorded in eDiary						
Shortness of breath (severity scale) ⁶	X	X	Self-reported by patient daily and recorded in eDiary					X	
Cough (severity scale) ⁷	X	X	Self-reported by patient daily and recorded in eDiary					X	
Pulse oximetry for oxygen saturation	X	X	Self-measured by patient daily and recorded in eDiary					X	
Prior and concomitant medications ⁸	X	updated	Recorded by clinician at telemedicine visit					X	Recorded by clinician at telemedicine visit
Adverse events			Self-reported by patient and recorded in eDiary, and recorded during telemedicine visit including severity and relationship to study drug, plus actions taken to treat AE or if drug discontinued					X	Recorded by clinician at telemedicine visit

Procedure	Screening Day -4 to -1	Day 1	Day 1	Days 2 and 3 ± 1 day	Days 4 to 9	Day 10 ± 1 day	Day 11	Day 12 ± 1 day	Day 28 ± 1 day
Clinic Visit #	1	If in clinic	If at home					2 or 3	
RT-PCR	X							X	
Hematology ⁹	X							X	
Blood chemistry ¹⁰	X							X	
Randomization		X	X						
Load eDiary to Patient Device, provide pulse ox device, thermometer, and instructions for use		X	X						
Dispense study drug ¹¹		X	X						
Study drug administration			X	Each day		X			
Medication compliance			eDiary	eDiary		eDiary			
Final drug accountability								X	

¹ A serum pregnancy test will be performed at screening and a urine or serum pregnancy test will be performed at Day 12.

² Vital signs include blood pressure and heart rate

³ COVID-19 symptoms will be assessed by designated clinical staff at in-clinic visits and will be checked at home by the patients and reported by the patient in the electronic diary (eDiary). Once the data is recorded in the diary it will be uploaded to the study database for clinician review.

⁴ Temperatures will be taken orally or on the skin surface and recorded in degrees Centigrade.

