7.3 Withdrawal Criteria

Patients are free to withdraw from the study at any time, without prejudice to their continued care.

Patients should have their Investigational Product withheld and continue to be followed for Safety per the protocol should any of the following events occur:

1. Patient develops an illness that would interfere with his/her continued participation.
2. Patient is noncompliant with the study procedures or medications in the opinion of the investigator. Patients who receive at least 1 dose of study drug should be followed for safety, if possible, until Day 28.
3. Patient takes prohibited concomitant medications as defined in this protocol.
4. There is confirmation of a pregnancy during the study, as evidenced by a positive pregnancy test.
5. The sponsor or a regulatory agency requests withdrawal of the patient.

Investigators should attempt to obtain information on patients in the case of withdrawal. For patients considered as lost to follow up, the investigator should make an effort (at least 1 phone call and 1 written message to the patient), and document his/her effort (date and summary of the phone call and copy of the written message in the source documents), to complete the final evaluation. All results of these evaluations and observations, together with a narrative description of the reason(s) for removing the patient, must be recorded in the source documents. The case report form (CRF) must document the primary reason for withdrawal.

If patients are hospitalized during the study period for anything other than being administratively registered in the hospital for observation, efforts should be made to continue the patient in the study

through Day 28. The Medical Monitor should assess the patient's ability to continue receiving study drug.

Investigators should contact the Medical Monitor, whenever possible, to discuss the withdrawal of a patient in advance.

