8.9 Important Administration Instructions

Patients will be instructed to:

- Administer study drug with food.
- Swallow the tablet(s) whole. Do not break, crush or chew the tablets.
- Complete the full course of study drug according to the schedule in [Table 1](#).

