9.3 Treatment Period

9.3.1 Week 1/Day 1 through Week 1/Day 3 (± 1 day for self-administration of study drug) – In-home

On Day 1, eligible patients will either return to the clinic or may have a telemedicine visit. Continued eligibility will be reviewed, and if eligible, patients will be randomized and will receive and self-administer 200 mg TQ or matching placebo on Days 1, 2, 3 ± 1 day. If the patient has an in clinic visit, s/he will be given sufficient study drug for the entire study. If the Day 1 visit is a telemedicine visit, the randomized blinded study drug will be sent via courier to the patient. Patients will be provided with an eDiary application (loaded onto a device of their choosing). The patient will self-administer study drug with food (per the label instructions [[Section 15.1](#)]) and record compliance in the eDiary. Patients will be provided an oral thermometer to check and record their daily temperature and a home pulse oximeter to record their daily oxygen saturation. Patients will record respiration rate, temperature, COVID-19 clinical signs including presence and severity of cough, respiration rate and shortness of breath, doctor's office and emergency room visits, AEs, and concomitant medications in the eDiary.

They will also record study drug administrations in the diary to monitor compliance. Daily diary data will be automatically uploaded to the electronic data management system and will be reviewed daily by clinical staff. Patients will be contacted by telephone or videoconferencing by designated study personnel on a daily basis to review AEs for severity by asking an open ended question, check for use of concomitant medications and more details such as dose, frequency, indication, and route of administration, and if there are new or worsening signs and symptoms of COVID-19 disease. Telephone interviews will follow a script and information will be recorded in source documents. If a suspected SAE or worsening of signs and symptoms of COVID-19 are reported, a study physician will be contacted to determine if the patient needs additional support (clinic visit, medication, or emergency room visit). If the patient cannot be reached an individual from their emergency contact list will be contacted to determine if the patient has been hospitalized.

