9.3.2 Week 1/Day 4 through Week 2/Day 9 – In-home

Patients will record presence/severity of cough, presence/severity of shortness of breath, respiration rate, temperature, O₂ saturation, AEs, and concomitant medications in the eDiary. Daily telemedicine phone calls or videoconferences from study site personnel will be conducted as described directly above.

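### The Section 10.4 immediate-stop rule for hemolysis and methemoglobinemia is not carried into Sections 7.3 and 8.9 or the daily-call physician trigger; the patient stop instruction is only in the appended label

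*Combined protocol and SAP*

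**What the plan says.** - **Section 10.4** gives the stop rule: "TQ should be discontinued immediately, if signs of hemolysis (anemia, dark colored urine) or methemoglobinemia (cyanosis) develop during administration". It also asks for monitoring for signs of hemolysis. It does not say who stops the drug, how a sign is reported, or within what time.
- **Section 7.3** introduces its list with "Patients should have their Investigational Product withheld and continue to be followed for Safety per the protocol should any of the following events occur". Five reasons follow: an interfering illness, noncompliance, prohibited medication, pregnancy, and a sponsor or regulator request.
- **Section 8.9** gives patients three instructions: take with food, swallow whole, and "Complete the full course of study drug according to the schedule in" Table 1.
- **Section 6.1**, repeated in 9.3.1 and the synopsis, sets the escalation step: "If a suspected SAE or worsening of signs and symptoms of COVID-19 are reported, a study physician will be contacted".
- **Section 9.3.1** has designated study personnel call daily to "review AEs for severity by asking an open ended question". Clinical staff review the uploaded diary daily.
- **Section 9.3.2** lists the diary content: "Patients will record presence/severity of cough, presence/severity of shortness of breath, respiration rate, temperature", followed by oxygen saturation, adverse events and medications.
- **Section 10.1.3** adds that "the investigator should review AEs reported in the eDiary employed in the study", with no time limit.
- **Table 1 in Section 6.2** has adverse events "recorded during telemedicine visit including severity and relationship to study drug, plus actions taken to treat AE or if drug discontinued".
- **Appendix A (Section 15.1)**, the label, says in its sections 5.1 and 5.3 that patients should be advised to stop the drug and seek medical attention for signs of either toxicity. Its counseling section and Medication Guide repeat the advice to seek help promptly; the Guide names darkened urine and bluish lips or skin.

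**The concern.** Drug is self-administered at home on Days 1, 2, 3 and 10. An immediate-stop rule therefore protects the patient only if the patient or the daily caller knows to act on the sign. Section 10.4 states the rule for investigators, but the instruction to patients points the other way (finish the course), and the caller's escalation rule is silent on these signs.

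What is at stake is one or more further doses after a warning sign. Section 3.3.2.3 gives a mean half-life of about 16.5 days, so a dose cannot be undone quickly, and holding the next dose is the practical lever. Section 10.4 itself warns that some hemolysis risk remains despite G6PD testing, and that hemoglobin falls have been seen in G6PD-normal patients.

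**Working it through.** The protocol states no figure on this point, so there is none to reproduce. The check sets the sections side by side and then sizes the gap.

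**Step 1. Does the operational text name either toxicity?**

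| Place | Items listed | Items naming either toxicity |
|---|---|---|
| 7.3, reasons to withhold drug | 5 | 0 |
| 8.9, patient instructions | 3 | 0 |
| 6.1 / 9.3.1, conditions for calling a physician | 2 | 0 |

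The interfering-illness reason in 7.3 could cover these signs, but only by judgement. These counts show where the rule is missing; they do not measure risk.

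**Step 2. Which other routes could stop the next dose?**

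- *Scheduled laboratory tests.* Table 1 has hematology at screening and Day 12 only. On the nominal schedule the second draw follows the Day 10 dose, so it cannot stop any of the four doses. Section 10.5 does not list methemoglobin.
- *Home oximetry.* Saturation is recorded daily and reviewed daily, so it is a genuine detection route, particularly for methemoglobinemia. No action threshold is stated.
- *Daily call.* Section 10.1.3.1 requires a general, nonleading adverse-event prompt at each call. A patient who mentions dark urine will be heard; the text does not say that the caller must then escalate it.
- *Suspected SAE.* Section 10.1.1.2 gives blood dyscrasias without hospitalization as an example of an important medical event, so a recognized sign can fire the trigger. Classing it as serious depends on medical judgement, and the caller need not be a physician.
- *Worsening COVID-19.* The Medication Guide lists shortness of breath as a sign of both toxicities. If it worsens, the trigger fires. Isolated dark urine would not fire it.
- *Investigator review and adverse-event recording.* Section 10.1.3 sets no deadline. Table 1 and Section 10.1.2 record a discontinuation but do not prompt one.

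What remains is a non-serious, isolated sign that the caller does not escalate before the next dose.

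**Step 3. How many patients?**

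Inputs: label section 6.1 reports hemolytic anemia at under 1% in 825 subjects with a mean exposure of 21 weeks; Section 12.6 plans 125 patients per arm; Section 6.1 plans about 275 enrolled, 1:1.

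- Expected count = rate × n. At the 1% ceiling: 0.01 × 125 = 1.25. With 275 randomized: 275 / 2 = 137.5, and 0.01 × 137.5 = 1.4.
- At an assumed 0.1%: 0.001 × 125 = 0.125.
- Chance of at least one case = 1 − (1 − rate)^125: 0.12 at 0.1% and 0.72 at 1%.

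The range is therefore 0 to about 1 tafenoquine patient, before restricting to signs that are non-serious and not escalated.

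Two other label rates are context only. Hemoglobin falls of at least 3 g/dL (2.3%; 0.023 × 125 = 2.9) are a laboratory finding. Raised methemoglobin (13%; 0.13 × 125 = 16) was asymptomatic. Neither is a rate of patient-visible signs, and the documents give none for dark urine or cyanosis.

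**The case against.** Section 10.4 is in force and binds investigators without being repeated elsewhere, and Section 7.3 does not call its list exclusive. Section 8.9 covers how to take tablets and is not offered as the whole of safety counseling. Contact is daily, and the escalation trigger needs only a suspicion of seriousness. Only G6PD-normal patients enroll, for four doses. The call script was not supplied and consent pages were removed before review; either could carry a stop-and-call instruction, so their absence here is not a defect in the plan.

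The label is the strongest counterpoint. A reader might infer from the gaps in 7.3, 8.9 and the trigger that nothing in the supplied protocol tells patients to stop, or that no route takes such a sign to a physician. The documents do not support either reading. Appendix A is part of the protocol and says to advise patients to stop and seek care. Inclusion criterion 7 and the dosing sections refer to the label, and the SAE definition can bring a recognized sign under the existing trigger.

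All of that stands, and it limits the point. It does not remove it. The body cites Section 15.1 for contraindications, excluded medication, taking the drug with food and further information. No study procedure requires the counseling or the Medication Guide to be given, and under Section 8.3 tablets are moved from blisters to bottles with labeling from the CRO.

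**Conclusion.** The point holds in a limited form and is minor. Sections 7.3 and 8.9 and the daily-call trigger do not carry the Section 10.4 stop rule, and the full-course instruction pulls against it. Existing routes should catch many cases. The residual gap is mainly an isolated, non-serious sign, such as dark urine, that a non-physician caller does not pass on before the next home dose.

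The size of 0 to about 1 of 125 tafenoquine patients assumes that the label's under-1% rate for hemolytic anemia applies. That could be too high, because the course is four doses rather than a mean of 21 weeks, or too low, because these patients are ill rather than healthy volunteers. The conclusion also assumes that the call script and consent form do not already close the gap. Efficacy conclusions are unaffected.

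**What to change.** 1. **Section 7.3:** add dark urine, symptomatic anemia and cyanosis, serious or not, as reasons to withhold blinded study drug, with a cross-reference to 10.4.
2. **Sections 6.1 and 9.3.1 (and the matching synopsis text):** add the same signs to the physician-contact trigger, and hold the next dose until a physician has reviewed the report.
3. **Section 8.9:** put a stop-and-call instruction for these signs next to the full-course instruction.
4. **Daily call:** ask about these signs specifically, but only after the open-ended, nonleading prompt that Section 10.1.3.1 requires, so that spontaneous reports are collected first.

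If the call script or consent form already covers any of this, align the protocol wording with it.

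The cost is protocol wording and a few scripted questions in a call that already takes place. No visits or tests are added. The downside is slightly longer calls and some extra solicited, non-specific adverse-event reports in both arms.
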